Study Title	Expanding use of continuous glucose monitoring beyond COVID in critical care: Impact on nurse work patterns and patient outcomes
NCT Number	N/A
Document Description	Study Protocol and Statistical Analysis Plan
Date	April 26, 2022

Research Protocol

Expanding use of continuous glucose monitoring beyond COVID in critical care: Impact on nurse work patterns and patient outcomes

I. Objectives

The **primary objective** of this mixed methods hybrid II implementation study is to assess the feasibility of real time continuous glucose monitoring (CGM) implementation using a CGM plus (+) point-of-care (POC) protocol among patients on IV insulin or those with hyperglycemia ($>250\text{mg/dl}$) in the critical care hospital environments. Use of the hybrid II implementation study design will allow simultaneous evaluation of implementation and effectiveness outcomes to promote more rapid adoption of CGM as routine care for hospitalized patients.

The research Questions (RQ) we hope to address in this study are:

RQ 1: Establish the clinical utility, fidelity, and adoption of Dexcom G6 CGM as a tool for making dosing decisions within a CGM+POC protocol among medical intensive care unit (MICU) patients. We will conduct a prospective observational cohort study among MICU patients using Dexcom G6 CGM therapy (N=100). *Clinical utility criteria:* Time to CGM validation within protocol parameters, mean percent of dosing decisions determined by CGM, changes in insulin dosing from standard guideline or outside standard times in response to alarm and/or trend data (as measured by manufacturer download data and corresponding electronic health record (EHR) documentation). *Fidelity criteria:* Proportion of times CGM used non-adjunctively/number of times non-adjunctive use indicated per protocol. *Adoption criteria:* Proportion of patients who consent to received initial CGM monitoring/number of patients eligible to receive initial CGM monitoring. **Hypothesis:** The majority of insulin dosing decisions will be made using non-adjunctive CGM and CGM will alter nursing dosing decisions from standard guidelines.

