The patient will remain on CGM for the duration of their hospital stay and if discharged to home may transition to personal use of the Dexcom G6. The Dexcom G6 sensor is replaced every 10 days and will be removed and then replaced for some radiographic procedures or sensor failure. CGM data is automatically transferred to Dexcom's cloud-based Clarity system.

Table 3. OSUWMC Hypoglycemia Guideline, Patients Who are Not Alert, Are NPO, or on IV Insulin Infusion

Blood Glucose (BG) Level*	Action	Follow-Up
60-79 mg/dL	
 • Administer 7.5 g Dextrose D50% (15 ml) IV* • Consider calling House Officer if patient experiencing recurrent BG <70 mg/dL in past 12 h 	
 • Recheck BG q 15 min following treatment and treat accordingly until ≥ 80mg/dl • Once ≥ 80mg/dl, recheck BG q1h x2 (x4 if <45mg/dL at onset), then resume POC glucose as previously ordered, Patients who are admitted with hypoglycemia should be monitored at least q 4h for a minimum of 24h
45-59 mg/dL	
 • Administer 12.5 g Dextrose D50% (15 ml) IV* • Call House Officer to report BG and action taken 	
<45 mg/dL	
 • Administer 25 g Dextrose D50% (15 ml) IV* • Call House Officer to report BG and action taken 	
ALL	
 • Consider adding Dextrose 5% to maintenance IV fluids at a rate of ≥ 50ml/hr or increase rate of existing maintenance IV if dextrose source already present 	
 • If > 4h from initial event and BG ≥ 80mg/dl for two consecutive readings, may consider reducing IV dextrose

Variables and measures. *Clinical utility criteria:* Time to CGM validation within hybrid protocol parameters, mean percent of dosing decisions determined by CGM, changes in insulin dosing from standard guideline or outside standard times in response to alarm and/or trend data (as measured by manufacturer download data and corresponding EHR documentation). *Fidelity criteria:* Proportion of times CGM used non-adjunctively/number of

times non-adjunctive use indicated per protocol. *Adoption criteria:* Proportion of patients approached to received CGM monitoring/number of patients eligible to receive initial CGM monitoring.

RQ 2: To assess the degree to which CGM implementation within the ICU environment effects nursing workload and care delivery.

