Rational/Approach. We will explore the impact of CGM therapy using a CGM + POC protocol on patient hospital outcomes and costs. Analyzes the economic aspects inpatient CGM on patient health and healthcare interactions, with a focus on the costs (inputs) and consequences (outcomes) of CGM will enable full understanding of implementation effects. We hypothesize that patients with CGM will experience shorter length of stay, lower cost of stay, will be more likely to discharge to home vs. SNF, have a lower 30-day readmission rate, and experience lower mortality/morbidity than matched patients receiving fingerstick POC.

Procedures. Data will be retrospectively extracted from the EHR for patients using CGM in the MICU (N=100) along with 100 historical controls. Data will be obtained from the EHR and billing department through an information warehouse request. Data from the time in motion study will be evaluated to extrapolate the economic impact of nursing personnel time spent for CGM vs. POC glucose monitoring and resources used in POC vs. CGM glucose monitoring.

Variables and Measures. *Hospital outcomes criteria* include the following: Length of stay [ICU, total stay], cost of stay, discharge level of care [home, SNF], morbidity, mortality and readmission rate at 30 days. We will conduct economic evaluation of the costs to deliver CGM implementation in the MICU. We will track resources needed for CGM implementation including personnel, training, facilities, materials, equipment, and other necessary inputs. In addition to resources used, we will expand analysis to evaluate nursing productivity and burden. *Resource outcomes criteria* include: nursing time spent in CGM vs. POC glucose monitoring and cost of CGM vs. standard POC glucose monitoring materials.

Table 2. Patient Participant Schedule of Activities

Aim	Concept	Variable	Frequency	Measure	
Aim 1	Clinical utility criteria	Time to CGM validation (Aim 1 only)	Sensor placement (Q10 days)	
 • EHR • Clarity download 	
		Mean percent of dosing decisions determined by CGM	Daily		
		Changes in insulin dosing from guideline or outside standard times in response to alarm and/or trend data	Daily		
Aim 1	Fidelity & Adoption Implementation criteria	Proportion of times CGM initiated or patient approached for study inclusion according to protocol/total number of initiations	Admission	
 • EHR • Study recruitment log 	

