Descriptive statistics of central tendency (range, mean, median, and standard deviation) will describe variable characteristics and examine data distribution for normality and outliers. Descriptive statistics will summarize the sample characteristics and distribution of each variable. Data will be screened for normality, outliers, and homogeneity. Continuous variables with normal distribution will be reported as mean (standard deviation) while non-normal distribution will be reported as median (interquartile range). For **RQ1**, multivariate linear models will be used to evaluate clinical utility and implementation variables while examining the effects of patient condition (i.e., sequential organ failure assessment (SOFA) score, renal replacement, ventilator support, pH) as covariates. For **RQ 2**, For qualitative analysis of focus group data, a code book will be developed a priori based on the semi-structured interview questions. Interview data, fieldnotes and memos were imported into NVivo 12.0 (Doncaster, Australia) for data management and analyzed using a qualitative descriptive approach.^{35,36} Two researchers ([name] and [name]) will perform qualitative analysis. Portions of text will be coded with terms that were low inference (“data close”); then grouped into thematic categories and subthemes.³⁵ For **RQ3**, hyperglycemic and hypoglycemic events will be identified for CGM and non-CGM users. Discrete CGM glucose values will be used to aggregate derived measures of glucose variability, including time in target (blood glucose value of 70-180mg/dl), time 100-180mg/dl (representing a more conservative target used inpatient), time 140-180mg/dl (representing institutions IV insulin guideline glycemic target), time above target (>180mg/dl & >250mg/dl), time in hypoglycemia (<70mg/dl & <55mg/dl), glucose standard deviation, and coefficient of variation. Daily percent time in target as well as cumulative time in target will be assessed. Time in target will be derived from ADA glucose targets defining hypoglycemia as a blood glucose less than 70mg/dl and peak post-prandial glucose as <180mg/dl³⁷. The blood glucose range of 70-180mg/dl is consistent with other studies examining time in target.³⁸⁻⁴¹ Measures of hypoglycemia will be in accordance with ADA recommendations for measurement at <70mg/dl and <55mg/dl which is a marker of severe hypoglycemia.⁴² Days with $\geq 70\%$ CGM percent wear, as recommended by ADA, will be included in daily time in target analysis.⁴² For matched historical control patients, percent POC in target (70-180mg/dl), 100-180mg/dl, 140-180mg/dl, percent POC >180mg/dl and percent POC >250mg/dl, percent POC <70mg/dl and percent POC <55mg/dl will be evaluated consistent with other recent studies.^{43,44} For CGM daily glycemic control (i.e., time in range [70-180mg/dl], time 100-180mg/dl, time 140-180mg/dl), linear mixed effect modeling (LMM) for repeated measures will be used to adjust for between subject and within subject variance. A 3-tiered LMM will be used to control for patient, unit, and nurse specific variability. LMM will be repeated for analysis of daily POC glucose control for matched historical control patients for days with ≥ 3 POC fingersticks performed. Two-sided significance level of 0.05 was used for all the statistical tests. For **RQ4**, the cost analysis for the proposed study will be conducted from the provider perspective. Cost estimation involves three major steps: (1) identify the relevant cost items; (2) measure the use of resources; and (3) place a value on the resources used. We will obtain estimated costs for proposed CGM implementation. Direct benefits and savings tend to fall into one of two categories: either savings from enhanced efficiency and productivity, or savings from outcomes improvement (e.g., reducing length of stay, lower 30 day readmissions). Costs that do not vary with the number of patients will be categorized as fixed costs, whereas those that vary by the number of patients will be defined as variable costs. The costs of the CGM implementation will be compared to costs under a control scenario. We will estimate the potential costs and cost savings resulting from the CGM implementation.

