- Any severe adverse event resulting in prolonged hospitalization, or other life-threatening complication that is attributed to the study intervention and is expected to recur

Patient participation in the study will stop if any of the following occur:

- Failed sensor validation x 2 sensors (48 hours)
- Transitioned to hospice care
- Patient participant or patient's legally authorized representative withdraw consent

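### RQ1 names only linear models for a validation time that the protocol's own exits censor, and for dosing outcomes repeated daily within patient

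*Combined protocol and SAP*

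**What the plan says.** Section III.D (Data Analysis) gives one inferential method for RQ1: "multivariate linear models will be used to evaluate clinical utility and implementation variables". The covariates are "sequential organ failure assessment (SOFA) score, renal replacement, ventilator support, pH) as covariates".

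Section III.C (RQ 1, Variables and measures) opens the list of clinical utility criteria with "Time to CGM validation within hybrid protocol parameters, mean percent of dosing decisions determined by CGM" and adds changes in insulin dosing. Fidelity is defined as "Proportion of times CGM used non-adjunctively/number of times non-adjunctive use indicated per protocol".

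The patient schedule of activities (the second table numbered 2) records validation time at each sensor placement. It lists "Mean percent of dosing decisions determined by CGM" and dosing changes as daily items.

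Section IV.E ends a patient's participation on "Failed sensor validation x 2 sensors (48 hours" (counted in hours from placement), on "Transitioned to hospice care", or on withdrawal of consent. The pilot benchmark in III.C accepts 16 of 20 patients validated within 24 hours, so the plan expects that some patients will not validate quickly.

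The plan does not say how a patient without a validation time enters the RQ1 model, how repeat sensors are counted, or whether daily values are averaged per patient or modelled by day. The same Data Analysis paragraph does specify a repeated-measures mixed model, but only for the daily glycemic outcomes of RQ3.

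**The concern.** A patient who leaves before validating has no validation time, only the knowledge that it exceeds the time observed. An ordinary linear model has no place for that information. The analyst must leave the patient out or insert a number, and both pull the mean towards faster validation. Exits caused by deterioration are also likely to be related to SOFA score, ventilation and pH, so the covariate effects that RQ1 sets out to examine could be distorted too.

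The dosing outcomes are proportions with varying denominators, repeated over days in the same patient. If the days are treated as independent observations, the standard errors do not reflect the number of patients.

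The protocol's primary objective is feasibility. How soon CGM becomes usable, and how often it drives dosing, are central results. RQ1 also hypothesises that most dosing decisions will rest on CGM, and that answer depends on whether never-validated patients are in the denominator.

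**Working it through.** **The plan's own figures.** None is stated for RQ1. The only power figures (80%, 99%, 90%) concern RQ3. They reproduce as 80.7%, 99.7% and 91.0%, and this point does not rest on them.

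**1. Time to validation.** From the documents: exit at 48 h, and a pilot benchmark of 80% validated by 24 h. Assumed: exponential times, with a share p of 80%, 90% or 95% validated by 24 h.

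- Rate λ = −ln(1 − p)/24; true mean = 1/λ.
- Share unvalidated at 48 h: S = (1 − p)².
- Mean with non-validators set to 48 h: R = (1 − S)/λ.
- Mean with non-validators dropped: (R − 48·S)/(1 − S).

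For p = 80%: λ = 1.609/24 = 0.0671 per hour; mean 14.91 h; S = 0.04; R = 14.91 × 0.96 = 14.32 h; dropped mean = (14.32 − 1.92)/0.96 = 12.91 h.

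| p by 24 h | True mean | Unvalidated at 48 h | Dropped | Set to 48 h |
|---|---|---|---|---|
| 80% | 14.91 h | 4% | 12.91 h (−13%) | 14.32 h (−4%) |
| 90% | 10.42 h | 1% | 9.94 h (−4.7%) | 10.32 h (−1%) |
| 95% | 8.01 h | 0.25% | 7.89 h (−1.5%) | 7.99 h (−0.3%) |

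Sensitivity to shape: validation needs two pairs about one hour apart, so times near zero cannot occur. With the exponential starting at 1 h, λ = −ln(1 − p)/23, the mean is 1 + 1/λ, S = exp(−47λ) and R = 1 + (1 − S)/λ. For p = 80% the mean is 15.29 h, S = 0.0373 and R = 14.76 h, so the dropped mean is (14.76 − 48 × 0.0373)/0.9627 = 13.47 h (−12%). For p = 95% the same steps give 8.57 h against 8.68 h (−1.2%). The picture does not change.

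**2. Repeated days.** The documents give neither days per patient (m) nor the intraclass correlation (ICC). Assumed: m = 3 to 10 and ICC = 0.1 to 0.5. If days are pooled as independent, the correct standard error for a patient-level quantity is √(1 + (m − 1)·ICC) times the naive one:

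- m = 3, ICC 0.1: √1.2 = 1.10
- m = 5, ICC 0.3: √2.2 = 1.48
- m = 10, ICC 0.5: √5.5 = 2.35

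A simulation of 100 patients (2,000 runs per setting, m = 3 to 7, ICC 0.1 to 0.5) gave these results for a nominal 5% test:

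- Pooled least squares, covariate constant within patient: 9% to 34% false positives.
- Patient-clustered standard errors, or one mean per patient: about 5% to 7%.
- Pooled least squares, covariate varying within patient (6 days, ICC 0.3): naive standard error about 1.19 times too large, 1.9% false positives.

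**3. Denominator for dosing decisions.** Suppose a share f never validates, and each patient contributes one percentage (assumed). A validator-only result must then exceed 50%/(1 − f) to be a majority among all enrolled. For f = 4% this is 50/0.96 = 52.1%; for f = 20%, 50/0.80 = 62.5%.

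**The case against.** The strongest reply is that the plan never says that non-validators are dropped or that patient-days are pooled. A mean percent can be read as one value per patient, and then standard errors are not understated. A linear model can carry clustered errors, and the authors clearly know mixed models. For the dosing outcomes this stands: the gap is one of specification, not a demonstrated error. It does not rescue time to validation, because any ordinary linear model needs a number for every patient it includes.

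A second reply is that skewed variables will be reported as medians. A median that ranks non-validators as late is unaffected while fewer than half are unvalidated. This helps the description, if non-validators are in fact ranked, but not the covariate model.

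Three stronger readings are tempting, and the documents do not support them.

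- **That mean validation time is understated by 40%.** Truncating at 24 h with 80% validated does give 14.91 − 24 × 0.2/0.8 = 8.9 h against 14.9 h. But participation runs to 48 h, so validations between 24 and 48 h are observed. Failure in 20% of participants at 24 h is also listed as a study-stopping condition, so it is a boundary case.
- **That tests on SOFA, renal replacement, ventilation and pH are anti-conservative.** This needs pooled days and covariates constant within patient. The schedule lists SOFA, dialysis, ventilation and pH as daily items, so the size of the error is unproven and its direction may be reversed.
- **That the feasibility decision as a whole leans towards success.** The pilot benchmark is a proportion of all participants and counts non-validators as failures. The lean applies only to the RQ1 model and to any validator-only summary.

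**Conclusion.** The point holds as a gap in the RQ1 analysis plan. The stated method does not suit a censored time, and the handling of non-validators, early exits, repeat sensors and repeated days is left open.

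If non-validators are dropped, the understatement of mean validation time runs from about 1.5% to 13% on the exponential assumption with the 48 h exit; setting them to 48 h gives 0.3% to 4%. It is negligible if nearly all patients validate. If some would never validate, no finite mean exists, and the validators' mean answers a narrower question.

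Errors in the standard errors are conditional on pooling patient-days. They are then too small by a factor of 1.1 to 2.35 for covariates constant within patient, and possibly too large for covariates that change by day. The validation-time distribution, days per patient and ICC are all assumptions. The change is worth making before the data are analysed, but the plan is not shown to produce a wrong feasibility conclusion.

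**What to change.** Replace the RQ1 sentence in Data Analysis with three specifications.

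1. **Time to validation.** Measure from insertion of the first sensor in every patient placed on CGM. Report the proportions validated by 24 h and 48 h and the cumulative incidence. Censor at 48 h or at the end of observation, and treat death, hospice transfer or withdrawal before validation as competing events. Use a time-to-event model, such as a cause-specific Cox model, for covariates. State whether validation on a replacement sensor within the 48 h counts. Summarise later placements, including those after imaging, separately or with clustering by patient.
2. **Share of dosing decisions by CGM, and fidelity.** Use a binomial GEE or mixed model on numerator and denominator counts, clustered by patient.
3. **All-enrolled summary.** Report dosing decisions with never-validated patients contributing zero CGM decisions, beside any validator-only figure.

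The cost is SAP wording and slightly more analysis, using data already scheduled for collection. If few patients fail to validate, the time-to-event covariate model may add little. The proportions, the cumulative incidence and the all-enrolled summary remain useful in either case.

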RQ 2: Assess the effects of CGM implementation on nursing workload and factors influencing nursing care delivery. We examine nursing workload and care delivery factors through surveys administered to MICU nurses and through a MICU staff nurse focus group (N=10). *Nursing care delivery factors:* Acceptability of CGM measured by the Acceptability of Intervention Measure (AIM), appropriateness of CGM measured by the intervention appropriateness measure (IAM), and feasibility, measured by the Feasibility of Intervention Measure (FIM). Nursing care delivery factors, evaluation of CGM support, and CGM knowledge will be evaluated through focus groups and CGM Satisfaction Questionnaire (modified for healthcare workers). **Hypothesis:** The use of CGM will significantly reduce nursing workload while increasing frequency of glucose monitoring.

RQ 3: To assess glycemic control among patients receiving CGM in the CGM enabled MICU compared to historical control patients who received POC glucose monitoring in the MICU. Among critically ill patients on CGM (N=100) we will examine time in range (70-180mg/dl), time 100-180mg/dl, time 140-180mg/dl, time in hypoglycemia ($<55\text{mg/dl}$, $<70\text{mg/dl}$), and time in hyperglycemia (180-250mg/dl, $>250\text{mg/dl}$) compared to matched historical control patients using 3-tiered linear mixed models to control for patient, unit, and nurse specific variability. **Hypothesis:** Patients with CGM will exhibit greater time in range (100-180mg/dl, 140-180mg/dl, 70-180mg/dl) and experience less frequent time in hypoglycemia than patients on fingerstick POC.

RQ 4: (exploratory) To assess hospitalization outcomes and conduct economic evaluation of the costs to deliver CGM implementation in the MICU. We will track time and resources needed for CGM implementation including personnel, training, facilities, materials, equipment, and other necessary inputs. *Hospitalization outcomes criteria:* Length of stay [ICU, total stay], cost of stay, cost of CGM vs. standard POC glucose monitoring, discharge level of care [home, SNF], 30-day readmission, morbidity, and mortality. **Hypothesis:** Patients with CGM will experience shorter length of stay, lower cost of stay, will be more likely to discharge to home vs. SNF,

have lower 30-day readmission rate, and experience lower mortality/morbidity than matched historical control patients receiving fingerstick POC in the MICU.

II. Background and Rationale

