A hybrid research design that combines elements of effectiveness and implementation research will be used to enable more rapid adoption of CGM as standard of care. Traditional step-wise approaches to research which progress from clinical efficacy research, to clinical effectiveness research, and finally implementation research limit application and slow routine uptake in real-world environments. A hybrid research II design allows for two objectives within the research with equal emphasis placed on (1) testing the effectiveness of the intervention and (2) determining feasibility and potential impact of the implementation strategy. The use of this design allows us to craft a blueprint for successful deployment of CGM therapy within health systems, while at the same time gathering valuable real-world effectiveness data. It also allows us to examine how clinical outcomes relate to levels of adoption and fidelity.

[figure not shown]

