Sample Size Justification. The primary outcome for the power analysis is the percentage of time spent in target (70-180mg/dl). We estimate from previous studies^{13,28} that these values may have a standard deviation as high as 25 percentage points, in which case with 100 patients in each group we will have 80% power to detect a difference of 10 percentage points in time in range (e.g., 65 vs. 75); a moderate effect size of 0.4. If the standard deviation is lower (e.g., 15 as has been true in some studies), we will have greater power (99%) to detect a 10 point difference and are still well powered to detect smaller differences (e.g., 90% power for a 7 point difference). All power calculations assume an alpha of 0.05 and minimal statistical effects of clustering within the hospitals (e.g., unit or nurse level).

C. Detailed study procedures

Recruitment: Critical care clinical research coordinators will screen for preliminary eligibility and forward potential participant names to study team using a secure medical record in-basket process. The study team will determine eligibility. The study team will ask for permission for the patient to be approached. If permission is granted, the study team will verify eligibility and obtain informed consent from the patient or the patient's legally authorized representative. Consent will be obtained prior to research participation and CGM placement. Recruitment is expected at a rate of 5 patients per week over seven months. Our target recruitment will be 100 MICU patients.

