Rational/Approach. We will conduct a mixed method analysis to evaluate nursing workload and care delivery factors. Nursing care delivery factors including evaluation of CGM support, acceptance of CGM, perceived feasibility, and CGM knowledge, will be evaluated using a combination of questionnaires and focus groups.

Procedures/Variables and Measures. We will evaluate *nursing care delivery factors* related to CGM implementation support, acceptance of CGM, feasibility, appropriateness, CGM knowledge and satisfaction with CGM as measured by Acceptability of Intervention Measure (AIM), Intervention Appropriateness Measure (IAM), and Feasibility of Intervention Measure (FIM), CGM Satisfaction Questionnaire (modified for healthcare workers) and focus group conducted among nurses in the CGM-enabled MICU. The AIM, IAM, and FIM are brief 5 item Likert-scale questionnaires with each showing a high degree of content validity with alphas for the 3 questionnaires between 0.87 and 0.89.³⁰ CGM Satisfaction Questionnaire (CGM-SAT) is a 44-item measuring satisfaction with CGM over the previous 6 months. The survey has a high degree of validity ($\alpha \geq 0.94$) in adults with type 1 diabetes using CGM.³¹ Several items will be modified for application in healthcare workers. All MICU staff nurses (N=152) will be informed of the study and invited to participate via email. Upon e-consent, the questionnaires will be administered via a REDCap survey. A focus group will be conducted among MICU staff nurses (N=10) to gage their experience using CGM. A semi-structured interview guide will focus on areas of perceived CGM implementation support and education, CGM knowledge, and recommendations for future best practice. All Aim 2 variables and measures appear in Table 2.

RQ 3: To assess glycemic control among patients receiving CGM in the CGM enabled MICU compared to historical control patients who received POC glucose monitoring in the MICU.

Rational/Approach. We will analyze glycemic control factors among MICU patients on CGM compared to 100 historical control patients from the same MICU who receiving only POC glucose monitoring. We hypothesis that patients with CGM will exhibit greater time in range (100-180 mg/dl, 70-180mg/dl, 140-180mg/dl) and experience less frequent time in hypoglycemia than patients on fingerstick POC.

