		Proportion of patients approached to received GCM monitoring/number of patients eligible to receive initial CGM monitoring	Admission		
		Acceptability of CGM			
		Appropriateness of CGM			
		Feasibility of CGM			
		CGM knowledge			
Aim 3	Patient condition	Demographic data: Age, race/ethnicity, gender	Admission	
 • EHR 	
		Height, weight, and BMI	Admission		
		Diagnosis and type of diabetes	Admission		
		Home diabetes regimen	Admission		
		Total daily insulin dose	Daily		
		Past medical history: tobacco use, COPD, hypertension, heart failure, coronary artery disease	Admission		
		Clinical condition: Admission/inpatient glucose, HbA1c, admission diagnosis, admitting service, MICU	Admission		

		location (North vs. South), DKA/HHS, sepsis, acute liver failure, acute heart failure		
		Clinical condition: SOFA score, dialysis, thromboembolic events, ECMO mechanical ventilation, ICU/hospital length of stay, cardiac arrest, cerebrovascular accident, mortality	Daily	
		Medications: vasopressor use, steroids, anticoagulants, acetaminophen dose	Daily	
		Creatinine, eGFR, ALT, AST, TBR, WBC, procalcitonin, ferritin, CRP, IL6, D-dimer, PTT, INR, troponin, pH, BHB, bicarbonate	Daily	
		Enteral or parenteral nutrition	Daily	
		O2 sat, pAO2, blood pressure	Daily	
Aim 3	Glycemic control	Time in target for CGM patients (70-180mg/dl)	Daily	
 • Clarity • EHR
		Time 100-180mg/dl for CGM patients	Daily	
		Time 140-180mg/dl for CGM patients	Daily	
		Time above range for CGM patients (>180mg/dl & >250mg/dl)	Daily	
		Time in hypoglycemia for CGM patients (<70mg/dl & <55mg/dl)	Daily	
		Percent POC in target (70-180mg/dl) (matched controls)	Daily	
		Percent POC 100-180mg/dl (matched controls)	Daily	
		Percent POC 140-180mg/dl (matched controls)	Daily	
		Percent POC above range (>180mg/dl & >250mg/dl) (matched controls)	Daily	
		Percent POC in hypoglycemia (<70mg/dl & <55mg/dl) (matched controls)	Daily	
		Glucose standard deviation	Daily	
		Glucose coefficient of variation	Daily	
Aim 4	Hospitalization outcomes and costs	Length of stay [ICU, total stay]	Discharge	
 • EHR • Clarity download
		Cost of stay	Discharge	
		Discharge level of care [home, SNF]	Discharge	
		Morbidity	Discharge	
		Mortality	Discharge	
		Readmission rate [30 days]	30d s/p discharge	
		Cost of CGM vs. standard POC glucose monitoring materials.	Discharge	

Table 3. Nurse Participant Schedule of Activities

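### RQ3's powered outcome is sensor time in range for CGM patients but percent of point-of-care readings for controls, and the analysis section writes no group term for the comparison promised in the objectives

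*Combined protocol and SAP*

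**What the plan says.** **Power.** Section III.B (Sample Size Justification) states: "The primary outcome for the power analysis is the percentage of time spent in target (70-180mg/dl". Taking an SD of 25 points, it says that "with 100 patients in each group we will have 80% power to detect a difference of 10 percentage points in time in range". At SD 15 it claims 99% power for 10 points and 90% for 7 points. The paragraph does not name RQ3, but RQ3 is the two-group analysis of time in range.

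**Outcome.** The Patient Participant Schedule of Activities lists "Time in target for CGM patients (70-180mg/dl" and, as a separate variable, "Percent POC in target (70-180mg/dl) (matched controls". Section III.D builds the CGM measures from discrete sensor values and admits days with at least 70% wear to the daily analysis. For controls it specifies "For matched historical control patients, percent POC in target (70-180mg/dl), 100-180mg/dl, 140-180mg/dl", with the corresponding shares above 180 and 250 and below 70 and 55 mg/dl, and models days with at least three fingersticks. It justifies percent POC by pointing to two recent studies. The hypoglycemia measures are split between sensor and POC in the same way.

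**Comparison.** Section I (RQ 3) says that CGM patients will be "compared to matched historical control patients using 3-tiered linear mixed models to control for patient, unit, and nurse specific variability". Section III.C (RQ 3) describes glycemic control "compared to 100 historical control patients from the same MICU who receiving only POC glucose monitoring". Section III.D fits the linear mixed model to the CGM patients' daily measures, then runs it again on the controls' POC data, and sets a two-sided 0.05 level. Section III.C says the data are merged before analysis. No pooled model, group effect or handling of matched sets is written.

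**Standing of RQ3.** Section III.A describes a hybrid design with "equal emphasis placed on (1) testing the effectiveness of the intervention".

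**The concern.** Every CGM patient is scored one way and every control the other. No covariate or random effect can then separate the effect of CGM on glucose from the effect of changing the ruler. A difference on the powered outcome, or the lack of one, could partly reflect how glucose was sampled.

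The model text adds a second problem. Two separate fits do not yield an estimated difference with a confidence interval, so the RQ3 estimate would be chosen later, possibly with the data in view. Because effectiveness carries equal weight with implementation, this affects a main result.

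**Working it through.** **1. Reproduce the plan's power.** Inputs from section III.B: n = 100 per group, alpha 0.05 (two-sided, from III.D), SD 25 or 15. SE = SD × √(2/100), which is 3.54 at SD 25 and 2.12 at SD 15. Power ≈ Φ(difference/SE − 1.96).
- 10 points, SD 25: Φ(2.83 − 1.96) = 80.7% (stated 80%).
- 10 points, SD 15: Φ(4.71 − 1.96) = 99.7% (stated 99%).
- 7 points, SD 15: Φ(3.30 − 1.96) = 91.0% (stated 90%).

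The arithmetic is sound, but it assumes one metric in both groups.

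**2. Set the two definitions side by side.**

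| | CGM patients | Historical controls |
|---|---|---|
| Instrument | Sensor | POC meter |
| Sampling | Every 5 minutes, up to 288 values a day | Clinical testing; schedule not given |
| Summary | Percent of time | Percent of readings, no time-weighting described |
| Day rule | At least 70% wear (0.70 × 288 = 201.6 values) | At least 3 fingersticks |

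A control day with three readings can score only 0, 33, 67 or 100%. POC timing can also depend on glucose: Table 3 (hypoglycemia guideline) calls for 15-minute and then hourly rechecks, and an unweighted percentage counts each one. For example, one low among six readings scores 1/6 = 16.7%, while a 30-minute low is 30/1440 = 2.1% of sensor time.

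**3. What an offset would do.** Let b be the difference between the metrics when true glucose is the same in both groups. With no true effect, P(reject) = 1 − Φ(1.96 − b/SE) + Φ(−1.96 − b/SE).

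| Assumed b | SD 25 | SD 15 |
|---|---|---|
| 0 | 5% | 5% |
| 1 | 6% | 8% |
| 3 | 14% | 29% |
| 5 | 29% | 65% |

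An offset against CGM costs power instead. At b = −2.25 and SD 25, power for 10 points is Φ(7.75/3.54 − 1.96) = 59%.

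**4. Can b be derived?** No. It depends on how controls were tested, which the documents do not say. Simulations with identical glucose in both groups show only that the answer turns on that schedule.
- One set assumed patient means of 165 mg/dl (SD 30), within-patient SD 45, a correlation time of 180 minutes and no measurement error. Sensor minus POC was 0.1 to 0.2 points with fixed 4- or 6-hourly testing, and 3.8 to 10.4 when testing stepped up to every 1 or 2 hours while out of range.
- Another set added sensor and meter error and used other glucose profiles. It gave −2.0 to +0.6 points with fixed testing and +0.3 to +7.5 when each interval followed the last reading.

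Nearly all inputs are assumed. The range includes zero and both signs.

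**5. What the missing group term leaves open.** If, for instance, the two fits were compared by whether their 95% intervals overlap (equal SEs), the effective alpha would be 2 × [1 − Φ(2 × 1.96/√2)] = 0.006. Power for 10 points at SD 25 would be Φ(2.83 − 2.77) = 52%. The plan does not say that this would be done, but it does not exclude it.

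**The case against.** The metric difference is disclosed and a precedent is cited. This is fair, and it means the plan is not hiding an inconsistency. The cited studies were not available here, so how far they support the choice cannot be judged. Precedent does not remove the confounding in any case.

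A reader might infer that the plan contains no between-group comparison. The documents do not support that: the objectives name the comparison and the model class, the data are merged, and a significance level is set. What stands is that section III.D does not carry the comparison through.

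A reader might also infer that the results are bound to favor CGM. That is not supported either. With regular control testing the offset may be negligible, and it could run against CGM.

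Feasibility is the stated primary objective, which tempers the point, although the design section gives effectiveness equal emphasis.

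The strongest objection is that a POC-based contrast is itself imperfect. Table 1 triggers extra POC tests in CGM patients only, so sampling still differs by group. In the simulations with measurement error, averaging POC values within 4-hour blocks left −3.0 to +0.9 points across control schedules, against −2.3 to +7.5 for the metrics as written. At −3.0 and SD 25, power for 10 points would be Φ(7/3.54 − 1.96) = 51%. The common metric therefore narrows the overall range and removes the difference in instrument, but it does not guarantee an unbiased result.

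**Conclusion.** The point holds. The powered RQ3 outcome is measured differently in the two groups, as are the hypoglycemia measures. Instrument, sampling pattern and day rule are fully confounded with group, and sections I and III.D must be reconciled on the model. These conclusions rest on the text and are firm.

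The size and sign of the bias are not established and may be near zero. The false-positive rates above are illustrations of assumed offsets, using the plan's sample size and its two SDs. The plan's power arithmetic is correct; the planned measurement does not match what it assumes.

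**What to change.** 1. Base the between-group RQ3 claim on POC values in both groups. Summarize them by one rule that limits over-counting of clustered or triggered readings, such as time-weighting or fixed-block averages. Apply one day-inclusion rule to both groups. Do the same for the measures below 70 and 55 mg/dl.
2. Fit one mixed model to both groups with a fixed CGM-versus-control effect, accounting for patient and matched set. Name its estimate and confidence interval as the RQ3 result, and align sections I and III.D.
3. Keep sensor time in range and sensor-detected lows as descriptive results for CGM patients, and do not test them against percent POC in controls.
4. Tabulate POC test frequency by group. State that residual bias may remain in either direction because Table 1 triggers extra tests in CGM patients only.
5. State the SD assumed for the POC metric and restate power on it.

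**Cost.** Section III.C (RQ 1) already calls for POC testing every 4 hours or more often in CGM patients. However, percent POC is listed as an RQ3 variable for controls only, so time-stamped POC values for CGM patients must be added to the extract. The rest is SAP wording and programming. Five-minute resolution is lost in the contrast, and lows between tests are missed in both groups. Power may fall slightly: if the SD rose 5.5% to 26.4, power for 10 points would be Φ(10/3.73 − 1.96), about 76-77% rather than 81%, and 80% would need 110 per group.
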